**Application of INTERCEED™ to the target incision site:**

- The size of INTERCEED™ should be sufficient to completely cover the target area (the incision size  $\leq$  8cm);
- Apply INTERCEED™ dry, in a single layer;
- It should be placed on denuded/injured surface (target incision site) to mechanically prevent this area from adhering to visceral surfaces, thus minimizing resultant adhesion formation;
- Do not fold, plug or apply multiple layers;
- INTERCEED™ adheres well to serosal tissue; it is not necessary to suture in place;
- Hold INTERCEED™ in place at site of application to ensure adherence;
- Moistening the INTERCEED™ with 1- 2 ml of irrigating saline solution (NaCl 0.9%) after positioning will further ensure its adherence and conformance to the application site;
- If moistening is desirable, this should be done only with solution (NaCl 0.9%) after INTERCEED™ is placed on the de-peritonealized serosal area cautiously keeping the fabric from floating off the surface;
- If floating off the surface occurs, the piece of INTERCEED™ should be discarded and a new piece used;
- If the product comes in contact with blood prior to use, it should be discarded because fibrin deposition on INTERCEED™ (ORC fabric) cannot be removed by irrigation and may promote adhesion formation;
- INTERCEED™ will be applied at the target incision to minimize possible dislodging during the remainder of the surgical procedure;

- Discoloration of the device to dark brown or black indicates incomplete hemostasis;
- If such discoloration occurs, it will happen within 1-2 minutes following application of INTERCEED™ and will reduce its effectiveness as an adhesion barrier and may promote adhesion formation;
- Should this discoloration occur, the device should be removed and complete hemostasis achieved before new piece of INTERCEED™ can be applied.

### **Postoperative Care:**

Postoperative care will be performed per institutional requirements for clinical practice or specific guidelines regarding postoperative care. Patient status is monitored closely until discharge. Changes in concomitant medications including analgesics will be recorded throughout inpatient stay.

### **Neoadjuvant radiation/chemotherapy and postoperative chemotherapy:**

The neoadjuvant radiation/chemotherapy and postoperative chemotherapy will be performed per institutional requirements for clinical practice or specific guidelines, except, abdominal radiotherapy between primary procedure and ostomy takedown (reversal). Patient status is monitored closely until discharge. The scope of neoadjuvant radiation is limited to pelvic cavity.

### **Ileostomy reversal + laparoscopic exploration:**

This surgery is the Phase 2 operation in this study. It is suggested that no more than three groups of surgeons at each site perform this surgery. During the surgery, the image data of the target incision of Phase 2 operation through laparoscopy should be recorded. The image data is defined as the videos which is not shorted than 30 seconds taken through laparoscopy

### **Screening**

Subjects will be consented prior to any actual study-specific screening procedures being conducted. Subjects will be considered enrolled into the study upon satisfaction of the following criteria:

- Completion of the informed consent process and signing the ICD;
- Verification of the eligibility criteria (Section 7.1) by the PI and/or authorized investigators. The verification must be conducted by the PI and/or authorized investigators prior to randomization.

### **Screening Failures**

Screened subjects who are not enrolled will be considered screen failures. For subjects who are determined to be screen failures, only the following data will be recorded on the eCRF:

- Informed consent date;
- Demographic information (age, race, gender, and ethnicity);
- Reason for screening failure.

### **Randomization**

Randomization will occur if the patient meets all inclusion criteria and does not meet any exclusion criteria.

Each case will be randomized to one of two groups in a 1:1 ratio. The only difference between the groups will be the use of INTERCEED™ or not. The plan is to randomize at least 110 subjects for each of the two groups. The randomization will be used in this study so that the patients cannot guess the upcoming assigned group.

The sponsor, will provide each site with computer-generated randomization envelopes, each bearing the subject randomization number, and containing the treatment allocation.

In the event a potential subject fails intra-operative criteria, and is not randomized to the study, the unused randomization envelope should be returned to the series, and used for the next subject per its original sequence

### **Visit 1 – Baseline/Screening Visit**

The following screening activities will occur prior to the study procedure:

- The subject must be given ample time to review and sign the ICD;
- Collection of demographic information (year and month of birth, race, gender, ethnicity, etc);
- Review and collection of medical/surgical history; especially the surgical history;
- Review/collection of inclusion/exclusion criteria and determination as to whether the subject is eligible for participation;
- Urine/blood pregnancy test;
- Physical Examination, including height, weight and abdominal sign;
- Concomitant therapy: including the dose and site of neoadjuvant radiotherapy;
- Concomitant medications: Only including the which used beyond two weeks. The neoadjuvant chemotherapy protocol and period should also be captured.
- Adverse Events;

### **Visit 2 – Randomization**

The following must be obtained in this visit:

- Randomization: whether the patients received neoadjuvant radiotherapy will be the factor of the stratified randomization.
- Confirm inclusion and exclusion criteria

### **Visit 3 – Phase 1 Operation**

The following must be obtained prior to the surgical procedure:

- Update to medical/surgical history
- Device usage data: The code and quantity of the used study product, placement position and placement method of the study product;
- Procedure time: the time beginning with the opening of the first incision to the closure of the last incision.
- Blood loss
- During this operation, adhesions assessment (extent and severity) and any treatment of adhesions will be recorded
- Quantity of surgical gloves used: including the surgical sterile gloves used by the doctors and instrument nurses;
- Length and closure method of the target incision: the sutures and closure method also should be recorded.
- Intra-operative device failure;
- Concomitant medications: Only including the medicine related to adverse events and which used beyond two weeks.;
- Concomitant therapy;
- Adverse Events;
- Defects of study product.

#### **Visit 4 – Post-Op through Discharge**

The following must be obtained in this visit:

- Concomitant medications: Only including the medicine related to adverse events and which used beyond two weeks. The postoperative chemotherapy protocol and period should also be captured (if any);
- Concomitant therapy;
- Adverse Events (Concomitant medication associated with AEs will also be collected);
- Defects of study product;
- Mechanical ileus;
- Physical Examination, including abdominal sign.
- SSI;
- All layer Wound dehiscence;
- Delayed wound healing events;.

## Visit 5 – Phase 2 Operation

The following information must be obtained in this visit:

- Review and collection of medical/surgical history: the surgical history should be collected carefully;
- Concomitant therapy;
- Physical Examination including abdominal sign;
- Concomitant medications: Only including the medicine related to adverse events and which used beyond two weeks. The postoperative chemotherapy protocol and period should also be captured (if any);
- SSI;
- All layer Wound dehiscence;
- Delayed wound healing events;
- Adverse Events (Concomitant medication associated with AEs will also be collected);
- Defects of study product;
- Mechanical ileus;
- Operative data: the image data of operation needs to be recorded as follow: starting from the upper left quadrant and proceeding clockwise to the lower left quadrant. If the incisional adhesion was found, whether and how the treatment for the adhesion performed should be recorded.

## Visit 6 – Post-Op through Discharge

The following must be obtained in this visit:

- Concomitant medications: Only including the medicine related to adverse events and which used beyond two weeks;
- Concomitant therapy;
- Adverse Events;
- Defects of study product;
- Mechanical ileus;
- Physical Examination including abdominal sign.
- SSI;
- All layer Wound dehiscence;
- Delayed wound healing events;

- Study completion: If this visit occurs 6-9months after Phase 1 operation, study completion would be conducted in this visit.

### **Visit 7 – 6-7 months after Phase 1 operation (Phone contact)**

If Visit 6 occurs 3-6 months after Phase 1 operation, this visit should be conducted. The following must be obtained in this visit:

- Review and collection of medical/surgical history: the surgical history and the diagnosis which may relate to abdominal adhesions should be collected carefully;
- Adverse Events;
- Defects of study product;
- Mechanical ileus;
- SSI;
- All layer Wound dehiscence;
- Delayed wound healing events;
- Study completion.

### **7.3. Monitoring Plan**

This study is performed according to the Good Clinical Practice for Medical Device Trials and related international laws and regulations, criteria, etc., such as ISO 14155, the Declaration of Helsinki.

The sponsor bears the monitoring responsibility for the clinical trial and will select the qualified monitor to execute the monitoring responsibility.

The monitor should comply with the related laws and regulations and the standard operating procedure established by the sponsor with regard to the monitoring to monitor each phase of this study.

The monitor should contact and visit the investigators at a regular basis and make the field visit/monitoring for the study. The monitor should make a visit when the first subject is enrolled, and make a necessary visit at a regular basis (about every 4 or 6 weeks) during the study period.

The monitoring includes the visit to clinical trial institution, verification of CRF data, communication with investigators and clinical trial institution, ensuring that this study will be performed strictly in compliance with the trial protocol and the requirements of regulations of Good Clinical Practice, etc.

The on-site inspection of CRF includes verifying the source document and checking whether original data is true, accurate, complete and clear, the original document of each subject is complete.

This study may be subject to the audit by the sponsor or regulatory authority. If such audit is

performed, the investigator must agree the auditor to look up the records of subjects. The investigator agrees the sponsor or its appointed representative and regulatory authority to monitor all project-related study documents on site by signing on the signature page of this trial protocol.

See the attached monitoring plan for the detailed monitoring plan.

## 8. STATISTICAL CONSIDERATIONS

### 8.1. Statistical Design, Method and Analysis Procedure

This study is a prospective, multicenter, randomized controlled study to evaluate the superiority of INTERCEED™ compared to blank control in reducing the incidence of postoperative incision adhesions in laparoscopic surgery.

The primary effectiveness endpoint is the proportion of subjects free of abdominal incision adhesions at primary target incision site observed in the two treatment groups (INTERCEED™ and Control). The assessment of adhesions will be conducted during the second laparoscopy for ileostomy reversal.

The statistical hypotheses for the primary endpoint are as follows:

- $H_0: P_I \leq P_C$  tested against the alternative hypothesis
- $H_a: P_I > P_C$

where  $P_I$  is the proportion of subjects free of adhesions in the INTERCEED™ group and  $P_C$  is the proportion of subjects with adhesions in the Control group.

The proportion of subjects free of adhesions will be summarized for each treatment group and will be calculated as the number of subjects free of adhesions divided by the total number of subjects randomized to that treatment. Within-treatment group two-sided 95% confidence intervals for the proportions of subjects free of adhesions will be provided using Clopper-Pearson method. In addition, a one-sided Wald 97.5% confidence interval for the difference in two independent proportions (INTERCEED™ minus Control) will be constructed and used for testing the null hypothesis of superiority stated above. If the lower limit of the confidence interval is greater than 0, then it will be concluded that INTERCEED™ is superior to Control.

The primary endpoint will be analyzed using the Intent-to-Treat (ITT) and Per-Protocol (PP) sets. The ITT analysis will be considered primary, while the PP analysis will be considered supportive. The analysis sets for this study are defined in section 8.9.

The following secondary effectiveness endpoints will be summarized descriptively by treatment group for the ITT analysis set:

- Extent and severity of adhesions--at the incision site and four abdominal quadrants;
- Incidence of subjects with mechanical ileus.

In addition, the following safety endpoints will be summarized descriptively by treatment group for the Safety analysis set:

- Incidence of subjects with surgical site infections (SSI) of target incision after Phase 1 operation;

- Incidence of postoperative all layer wound dehiscence of target incision after Phase 1 operation;
- Incidence of subjects with delayed wound healing events of target incision after Phase 1 operation;
- Any adverse event;
- Defects of study product.

All continuous variables will be summarized by number of subjects, mean, standard deviation, median, minimum and maximum. All categorical data will be summarized by frequencies and associated percentages.

All analyses/summaries will be produced using SAS® (Version 9.1 (EG) or later).

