#### 7.1.2. Trial Endpoint

##### Primary Endpoints

The primary endpoint is defined as the proportion of subjects with adhesions at the target incision site in each study group.

The assessment of adhesions will be conducted during the second laparoscopy for ileostomy reversal.

The primary endpoint will be assessed by means of reviewing the imaging data by independent central reviewers who will be blinded to the study treatment groups. The image data is defined as the video which is not shorter than 30 seconds taken through laparoscopy during Phase 2 operation and allowing an observation of the entire product application site and surrounding areas in the treatment group or the target incision site in the control group.

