## 8.5. Criterion of Acceptability/Unacceptability of Clinical Trial Result

For the primary efficacy endpoint, a one-sided Wald 97.5% confidence interval for the difference in proportions of subjects with adhesions (INTERCEED™ minus Control) will be constructed and used for testing the null hypothesis of superiority stated in section 8.1. If the upper limit of the confidence interval is smaller than 0, then it will be concluded that INTERCEED™ is superior to Control.

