## **8.7. Statistical Method of All Data, together with the Handling Method of Missing, Unused and Error Data (including Termination and Withdrawal Halfway) and Unreasonable Data**

All study endpoints will be analyzed using the available data. There will be no missing data imputation in this study.

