3.3 Effectiveness Endpoints Analysis

3.3.1 Primary Effectiveness Endpoint Analysis

The primary effectiveness endpoint is the proportion of subjects free of incision adhesions at the main target incision site observed in the two groups (experimental group and control group). The ITT and PP analysis sets will be used to analyze the primary effectiveness endpoint. The ITT analysis will be regarded as the primary analysis, and PP analysis as supportive analysis.

The statistical hypotheses for the primary endpoint are as follows:

- $H_0: P_I \leq P_C$
- $H_a: P_I > P_C$

Where P_I is the proportion of subjects free of adhesions in the experimental group, and P_C is the proportion of subjects free of adhesions in the control group.

The proportion of subjects free of adhesions in each treatment group will be summarized and calculated as: number of subjects free of adhesions divided by the total number of subjects randomized to receive the treatment. The two-sided 95% confidence interval for the proportion of subjects free of adhesions in the treatment groups will be provided by the Clopper-Pearson method. In addition, the two-sided Wald 95% confidence interval for the difference of two independent proportions (experimental group minus control group) will be constructed and used to test the null hypothesis for the superiority. If the lower limit of the confidence interval is greater than 0, it can be concluded that the experimental group is superior to the control group.

```
proc freq data =data;
  weight count;
  tables group*outcome / riskdiff(CL=WALD);
run;
```

Furthermore, a sensitivity analysis for the primary endpoint will be added. The stratification factor “presence or absence of neoadjuvant radiotherapy” will be adjusted to estimate the rate difference of the two groups and corresponding 95% CI.

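### The primary proportion is divided by all randomised subjects, against the plan's own available-data rule and its 77-evaluable-per-arm power; Protocol 8.1 also misdefines P_C

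*Protocol*

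**What the plan says.** **Denominator.** Protocol 8.1 calculates the proportion free of adhesions in each arm as the number free "divided by the total number of subjects randomized to that treatment". SAP 3.3.1 repeats this. Both documents define the ITT set, which is primary, as all randomised subjects. Protocol 8.7 then states that "All study endpoints will be analyzed using the available data" and rules out imputation. SAP 2.3.5 also excludes imputation from the primary analysis and adds multiple imputation as a sensitivity analysis. Protocol 8.2.1 and SAP 1.3.3 derive 77 per arm for 90% power and enrol 110 per arm to allow for 30% dropout. Protocol 8.6 and SAP section 4 treat those 77 per arm as subjects with an evaluable primary endpoint.

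**Hypothesis.** In Protocol 8.1, P_I "is the proportion of subjects free of adhesions in the INTERCEED™ group", but P_C "is the proportion of subjects with adhesions in the Control group". In SAP 3.3.1, P_C "is the proportion of subjects free of adhesions in the control group".

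**Scale.** Protocol 8.1 says: "The primary effectiveness endpoint is the proportion of subjects free of abdominal incision adhesions at primary target incision site". It concludes superiority if the lower limit of INTERCEED minus Control exceeds 0. Protocol 7.1.2 instead says: "The primary endpoint is defined as the proportion of subjects with adhesions at the target incision site in each study group". Protocol 8.3 and 8.5 also use the with-adhesions scale, and their rule reads: "If the upper limit of the confidence interval is smaller than 0, then it will be concluded that INTERCEED™ is superior to Control".

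**The concern.** A subject with no Phase 2 video cannot enter the numerator of the proportion free of adhesions. If that subject stays in the denominator, the analysis has in effect imputed an unfavourable outcome, although the plan says nothing is imputed. With 30% of subjects expected to lack the endpoint, this alters the estimate, the confidence limit and the power. Two analysts could each follow a written instruction and reach different verdicts on a registration endpoint.

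The P_C definition adds a second fault. As written, the null and alternative compare subjects free of adhesions in one arm with subjects who have adhesions in the other, which is not a treatment comparison. Sections 8.3 and 8.5 both refer back to that hypothesis.

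**Working it through.** **Inputs.** Adhesion rates 0.50 (INTERCEED) and 0.75 (Control), so free rates 0.50 and 0.25; one-sided alpha 0.025; power 90%; 77 evaluable and 110 enrolled per arm; dropout 30% (Protocol 8.2.1 to 8.4, SAP 1.3.3). The decision rule is the Wald interval with z = 1.96.

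**1. The plan's own figure.** With pooled variance under the null and mean rate 0.625:

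n = [1.96 × √(2 × 0.625 × 0.375) + 1.2816 × √(0.50 × 0.50 + 0.75 × 0.25)]² / 0.25² = 76.7, so 77 per arm.

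Power at 77 is 90.1%, and 77 / 0.70 = 110. The stated sample size is reproduced. Free rates of 0.50 and 0.25 give the same result, so the choice of scale does not affect it.

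**2. Power under each denominator.** Exact power of the Wald rule is the sum of binomial probabilities over all outcomes where the lower limit exceeds 0.

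| Denominator | Rates entering the comparison | Exact power |
|---|---|---|
| 77 evaluable per arm | 0.50 vs 0.25 | 0.909 |
| 110 randomised, exactly 77 evaluable per arm | free counts from 77, divided by 110 | 0.873 |
| 110 randomised, each subject missing with probability 0.30 | 0.70 × 0.50 = 0.35 vs 0.70 × 0.25 = 0.175 | 0.852 |

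Normal approximation for the last row: SE = √(0.35 × 0.65/110 + 0.175 × 0.825/110) = 0.0581; 0.175/0.0581 − 1.96 = 1.05; Φ(1.05) = 0.85.

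**3. Effect on a verdict.** Illustrative counts: 110 randomised and 77 evaluable per arm, with 62 vs 50 free.

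- Over 110: 0.564 − 0.455 = 0.109, SE 0.0670, lower limit 0.109 − 1.96 × 0.0670 = −0.022. Superiority not shown.
- Over 77: 0.805 − 0.649 = 0.156, SE 0.0707, lower limit 0.156 − 1.96 × 0.0707 = +0.017. Superior.

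**4. The two scales.** On a common set of evaluable subjects, the with-adhesions difference is minus the free difference and the Wald SE is identical. Upper limit below 0 is therefore the same event as lower limit above 0. Enumerating all 78 × 78 = 6,084 outcomes with 77 per arm gives no disagreements. The equivalence needs the two proportions to sum to 1 in each arm, which fails if subjects without an outcome stay in the denominator.

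**5. Literal P_C.** For 38/77 vs 58/77 with adhesions, free in INTERCEED minus with in Control is 39/77 − 58/77 = −0.247. The like-for-like free difference is 39/77 − 19/77 = +0.260. The written pair points the wrong way on data close to the design assumption.

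**The case against.** The best defence is that the documents, read together, lean towards evaluable subjects. SAP 2.1 makes subjects without missing data the default denominator for percentages. SAP 2.3.5 excludes imputation from the primary analysis. The interim formula in SAP section 4 counts subjects with an evaluable endpoint. The SAP's frequency-table code would normally leave out records with a missing outcome. This is fair, but it does not settle the matter: the SAP 2.1 default yields where something else is specified, and SAP 3.3.1 specifies all randomised.

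On P_C, the defence largely stands. The sentences that follow in 8.1 calculate the proportion free in both arms, and SAP 3.3.1 defines P_C correctly.

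Three stronger readings are tempting and are not supported.

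- **That 8.1 and 8.3/8.5 are rival success rules giving opposite conclusions.** The later sections reverse both the scale and the limit, so they mirror 8.1 on evaluable subjects. Section 7.1.2 changes the scale but contains no decision rule.
- **That 8.5 counts missing subjects as adhesion-free.** Putting 15/110 against 27/110 gives an upper limit of −0.006, and the corresponding power at the design rates would be about 75%. But 8.5 states no denominator, so these figures require carrying over the one from 8.1.
- **That the misdefined P_C wrecks the type I error.** Taken literally, with 30% adhesions in both arms and 77 per arm, it would declare superiority with probability 0.999. No passage directs anyone to run that analysis.

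**Conclusion.** The point holds in two parts of unequal weight.

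The main part is a real contradiction over the primary denominator. Followed literally, the all-randomised denominator gives about 85% power (about 87% if exactly 77 of 110 per arm are evaluable) in place of the stated 90%, and it can turn a superior result into one where superiority is not shown. The power figures assume the design rates and missingness unrelated to arm and outcome. The 62 vs 50 example is a chosen borderline case: it shows that the verdict can change, not how often it would. In that example neither denominator points to INTERCEED being worse.

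The lesser part is the P_C definition and the mixed endpoint scale. Both are drafting errors that should be corrected, and neither affects the sample size of 77 per arm.

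**What to change.** 1. In Protocol 8.1, define P_C as the proportion free of adhesions in the Control group, as SAP 3.3.1 does.
2. Use one scale in Protocol 7.1.2, 8.1, 8.3 and 8.5 and in the SAP: free of adhesions, INTERCEED minus Control, superior if the lower limit is above 0.
3. State one primary denominator in Protocol 8.1 and SAP 3.3.1 before database lock. Randomised subjects with an evaluable Phase 2 assessment would match Protocol 8.7, SAP 2.3.5 and the power calculation. The drawback is that this is a complete-case analysis. Several withdrawal criteria in Protocol 7.1.5 are post-randomisation events that may be related to outcome, such as an operation for obstructive ileus without the required video. The multiple-imputation sensitivity analysis should therefore be kept.
4. If all randomised is kept instead, state that a missing assessment counts as not free of adhesions, reconcile this with Protocol 8.7 and SAP 2.3.5, and restate power as about 85%.

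The cost is wording in both documents, plus one restated figure under option 4. No new data or subjects are needed.
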